8.6 Statistical Methods

To control the overall type I error rate at $\alpha = 0.025$ (1-sided) and since success of the trial requires success on 3 hypotheses (2 noninferiority and 1 acceptability), each individual hypothesis test will be evaluated at $\alpha = 0.025$ (1-sided).

For the safety analyses, unless otherwise specified, all statistical tests will be conducted at $\alpha = 0.05$ level (2-sided).

8.6.1 Statistical Methods for Immunogenicity Analysis

8.6.1.1 Noninferiority of Postvaccination 1 VZV Antibody Response (Primary Hypothesis 1)

For the primary hypothesis concerning the noninferiority of the Postvaccination 1 antibody response rate for recipients of VARIVAXTM PE34 process compared with VARIVAXTM (2016 commercial product), a 1-sided test for noninferiority in 2 binomial proportions will be performed at the $\alpha = 0.025$ (1-sided) level.

The statistical hypothesis that will be evaluated is:

 $H_0: p_1 - p_2 \leq -\delta$ versus $H_1: p_1 - p_2 > -\delta$,

where H_0 is the null hypothesis, H_1 is the alternative hypothesis, p_1 and p_2 are the true antibody response rates for the subjects in VARIVAXTM PE34 process and control groups, respectively, and δ is the pre-specified difference between the 2 proportions. The pre-specified difference between the 2 proportions (δ) is 0.10 (10 percentage points).

This analysis will be unstratified and the test statistic, p value, and corresponding 95% CIs will be calculated using the Miettinen and Nurminen method, an unconditional, asymptotic method [17]. The response rate in subjects receiving a single dose of VARIVAXTM PE34 process will be considered noninferior to the control group if the 1-sided p value for the associated noninferiority test is <0.025. This criterion is equivalent to requiring the lower bound of the 2-sided 95% CI for the difference in rates (Group 1 minus Group 2) exclude a decrease of 10 percentage points or more.

This analysis will be conducted on the PP population and the FAS population; however, the PP population is the primary population for the assessment of the hypotheses.

8.6.1.2 Noninferiority of Postvaccination 1 VZV Antibody GMT (Primary Hypothesis 2)

For the secondary hypothesis concerning the noninferiority of the Postvaccination 1 VZV antibody, GMT for recipients of VARIVAXTM PE34 process compared with VARIVAXTM (2016 commercial product), a 1-sided test for noninferiority in the VZV antibody GMT will be performed at the $\alpha = 0.025$ level (1-sided).

The statistical hypothesis for the noninferiority of the antibody GMT is:

H₀: $GMT_1/GMT_2 \le 0.67$ versus H₁: $GMT_1/GMT_2 > 0.67$,

where GMT₁ is the GMT for recipients in Group 1 receiving VARIVAXTM PE34 process and GMT₂ is the GMT for recipients in Group 2 receiving VARIVAXTM (2016 commercial product). A ratio of 0.67 corresponds to a 1.5-fold decrease in GMT in Group 1 compared with Group 2. Rejecting the null hypothesis (H₀) at the 1-sided $\alpha = 0.025$ level corresponds to the lower bound of the 2-sided 95% CI for the GMT ratio (Group 1/Group 2) being >0.67.

The GMT ratio (VARIVAX[™] PE34 process/VARIVAX[™] [2016 commercial product]) along with a 2-sided 95% CI and *p* value will be determined at week 6 Postvaccination 1. Assuming normality of the log antibody titers, a 2-sided 95% CI for the difference in the means of the log titers (VARIVAX[™] PE34 process minus VARIVAX[™] [2016 commercial product]) will be constructed based on the t-distribution. The CI of the GMT ratio (VARIVAX[™] PE34 process/VARIVAX[™] [2016 commercial product]) will then be provided by exponentiating the endpoints of the CI for the difference in log titers.

This analysis will be conducted on the PP and FAS populations; however, the PP population is the primary population for the assessment of the hypotheses.

8.6.1.3 Acceptability of Immune Response (Primary Hypothesis 3)

The primary hypotheses also involve whether or not subjects in Group 1 of VARIVAXTM PE34 process demonstrate an acceptable antibody response Postvaccination 1 to VZV (Hypothesis 3). An acceptable antibody response to VZV is defined as a response rate that is at least 76.0%. A hypothesis of H₀: $p \le p_0$ will be tested against the alternative H₁: $p > p_0$, where p is the antibody response rate after a single dose and p_0 is the hypothesized rate to be ruled out (76.0% for VZV). A 1-sided, 1-sample exact binomial test will be conducted at $\alpha = 0.025$ significance level. Rejection of the null hypothesis will lead to a conclusion of an acceptable antibody response to VZV. This is equivalent to the lower bound of the 1-sample 2-sided 95% CI being >76.0%. The 1-sample 2-sided CIs will be computed using the exact CI method for a single binomial proportion given in Collett [18].

This analysis will be conducted on the PP population and the FAS population; however, the PP population is the primary population for the assessment of the hypotheses.

The strategy to address multiplicity issues with regard to multiple primary immunogenicity endpoints and primary immunogenicity hypotheses is described in Section 8.8 – Multiplicity.

8.6.1.4 Secondary Summaries

In addition to the analysis described in Sections 8.6.1.1, 8.6.1.2, and 8.6.1.3 supporting the primary hypotheses, the following supportive summaries and figures will be presented for all subjects in the PP and FAS populations (where noted) with Postvaccination 1 immunogenicity data collected:

- The observed VZV antibody response rates (the percent of subjects with VZV titer ≥5 gpELISA units/mL) will be summarized by vaccination group at Postvaccination 1, along with 2-sided 95% CIs. The CIs will be computed using the exact CI method for a single binomial proportion given in Collett [18]. This will be computed on the PP population of subjects (with baseline antibody titer restriction) and the FAS population (with baseline antibody titer restriction).
- The observed VZV seroconversion rate (the percent of subjects with VZV titer ≥1.25 gpELISA units/mL) will be summarized by vaccination group at Postvaccination 1, along with 2-sided 95% CIs. The CIs will be computed using the exact method for a single binomial proportion given in Collett [18]. This will be computed on the PP population of subjects (with baseline antibody titer restriction) and the FAS population (with baseline antibody titer restriction).
- The observed VZV GMTs will be summarized by vaccination group at Postvaccination 1, along with 2-sided 95% CIs. The GMTs will be calculated by taking the natural log-transformation of the antibody titer, computing the arithmetic mean, and back-transforming. The CIs for the GMTs will be based on the natural log-transformed titers and the t-distribution. This will be computed on the PP population of subjects (with baseline antibody titer restrictions) and on the FAS population (with baseline antibody titer restrictions).
- For subjects who are seropositive at baseline (≥1.25 gpELISA units/mL for VZV), the following parameters and 95% CIs will be summarized at Postvaccination 1 by vaccination group: the GMT, the antibody response rate, the GMFR from baseline, and the percent of subjects with ≥4-fold rise in antibody titer from baseline. Similar methodology, as described previously, will be used for this summary. This will be computed on the PP and FAS populations (in subjects with baseline VZV antibody titer ≥1.25 gpELISA units/mL). The CIs will only be calculated if there are at least 5 subjects who are seropositive to a respective antigen.
- For subjects in the PP population only, graphical displays of the reverse cumulative distribution function of antibody titers will be illustrated by vaccination group.

The key immunogenicity analyses are summarized in Table 3.

Primary vs Supportive Approach†	Statistical Method	Analysis Population	Missing Data Approach
P (PP) S (FAS)	Miettinen and Nurminen‡ approach; tested at $\alpha = 0.025$ (1-sided); corresponding 95% CIs for risk difference	PP FAS	Observed data only
P (PP) S (FAS)	2-sample mean difference and 95% CI and p values based on log-transformed titers and t-distribution	PP FAS	Observed data only
			1
P (PP) S (FAS)	Exact 1-sample binomial; tested at $\alpha = 0.025$ (1- sided); corresponding 95% CIs	PP FAS	Observed data only
P (PP) S (FAS)	Exact 1-sample binomial methodology, 95% CIs	PP FAS	Observed data only
P (PP) S (FAS)	1-sample mean and 95% CI based on log-transformed titers and t-distribution	PP FAS	Observed data only
P (PP) S (FAS)	For rates, 1-sample binomial methodology, 95% CI For continuous variables, one-sample mean and 95% CI based on t- distribution	PP FAS	Observed data only
	Supportive Approach [†] P (PP) S (FAS) P (PP) S (FAS) P (PP) S (FAS) P (PP) S (FAS) P (PP) S (FAS) P (PP) S (FAS)	Supportive Approach†Statistical MethodP (PP) S (FAS)Miettinen and Nurminen‡ approach; tested at α = 0.025 (1-sided); corresponding 95% CIs for risk differenceP (PP) S (FAS)2-sample mean difference and 95% CI and p values based on log-transformed titers and t-distributionP (PP) S (FAS)Exact 1-sample binomial; tested at α = 0.025 (1- sided); corresponding 95% CIsP (PP) S (FAS)Exact 1-sample binomial; tested at α = 0.025 (1- sided); corresponding 95% CIsP (PP) S (FAS)Exact 1-sample binomial methodology, 95% CIsP (PP) S (FAS)1-sample mean and 95% CI based on log-transformed titers and t-distributionP (PP) S (FAS)For rates, 1-sample binomial methodology, 95% CI For continuous variables, one-sample mean and 95% CI based on t-	Supportive Approach†Statistical MethodAnalysis PopulationP (PP) S (FAS)Miettinen and Nurminen‡ approach; tested at α = 0.025 (1-sided); corresponding 95% CIs for risk differencePP FASP (PP) S (FAS)2-sample mean difference and 95% CI and p values based on log-transformed titers and t-distributionPP FASP (PP) S (FAS)Exact 1-sample binomial; tested at α = 0.025 (1- sided); corresponding 95% CIsPP FASP (PP) S (FAS)Exact 1-sample binomial; tested at α = 0.025 (1- sided); corresponding 95% CIsPP FASP (PP) S (FAS)Exact 1-sample binomial; methodology, 95% CIsPP FASP (PP) S (FAS)1-sample mean and 95% CI based on log-transformed titers and t-distributionPP FASP (PP) S (FAS)For rates, 1-sample binomial methodology, 95% CI For continuous variables, one-sample mean and 95% CI based on t-PP FAS

Table 3 Analysis Strategy for Key Immunogenicity Variables

8.6.2 Statistical Methods for Safety Analysis

Safety and tolerability will be assessed by clinical review of all safety data collected throughout the trial.

The analysis of safety results will follow a tiered approach (Table 4). The tiers differ with respect to the analyses that will be performed. Safety parameters or adverse experiences of particular interest that are identified a priori constitute "Tier 1" safety endpoints that will be subject to inferential testing for statistical significance with p values and 95% CIs provided for between-group comparisons. Other safety parameters will be considered Tier 2 or Tier 3. Tier 2 parameters will be assessed via point estimates with 95% CIs provided for between-group comparisons; only point estimates by vaccination group are provided for Tier 3 safety parameters.

Any adverse experiences (specific terms as well as system organ class [SOC] terms) that are not pre-specified as endpoints of particular interest will be classified as belonging to Tier 2 or Tier 3, based on the number of events observed. Membership in Tier 2 requires that at least 4 subjects in any vaccination group exhibit the event; all other adverse experiences will belong to Tier 3.

The threshold of at least 4 events was chosen because the 95% CI for the between-group difference in percent incidence will always include zero when treatment groups of equal size each have less than 4 events and, thus, would add little to the interpretation of potentially meaningful differences. Because many 95% CIs may be provided without adjustment for multiplicity, the CIs should be regarded as a helpful descriptive measure to be used in review, not a formal method for assessing the statistical significance of the between-group differences in adverse experiences and predefined limits of change.

For this protocol, the following are considered Tier 1 events: elevated temperatures (maximum reported temperature $\geq 102.2^{\circ}$ F [$\geq 39.0^{\circ}$ C] oral equivalent) within Days 1 to 42 after each vaccination; vaccine-specific measles-, rubella-, varicella-, zoster-like rashes, mumps-like symptoms, and injection-site rashes occurring within Days 1 to 42 after each vaccination; and solicited injection-site reactions (redness, swelling, pain/tenderness) within Days 1 to 5 after each vaccination. In addition, the broad clinical categories consisting of the percentage of subjects with any adverse experience, a vaccine-related adverse experience, a serious adverse experience, an adverse experience that is both vaccine-related and serious, and who discontinued due to an adverse experience will be considered Tier 2 endpoints. The *p* values (Tier 1 only) and 95% CIs (Tier 1 and Tier 2) will be provided for between-group differences in the percentage of subjects with events; these analyses will be performed using the Miettinen and Nurminen method, an unconditional, asymptotic method [17].

Extended Safety Follow-up Period (Day 133 [+14 days] to Day 271 [+14 days])

For the extended safety follow-up period, a summary will be provided of the number of subjects in each vaccination group who report a serious adverse experience or a medically attended adverse experience. For this extended safety follow-up period, these events will be treated as Tier 2 events, with 95% CIs being presented for the between-group risk differences in the percentage of subjects reporting these events. For serious adverse experiences, a

summary along with a between-group comparison will also be provided for the entire trial (i.e., from enrollment through 180 days Postvaccination 2).

Because many 95% CIs may be provided without adjustment for multiplicity, the CIs should be regarded as a helpful descriptive measure to be used in review, not a formal method for assessing the statistical significance of the between-group differences in adverse experiences.

Safety Tier	Safety Endpoint [†]	p Value	95% CI for Treatment Comparison	Descriptive Statistics
	Rate of elevated temperatures (≥ 102.2°F [39.0°C]) [‡] from Days 1 to 42 postvaccination	Х	X	Х
Tier 1	Vaccine-specific systemic rashes (measles-like, rubella-like, varicella- like, zoster-like), mumps-like symptoms, and injection-site rashes Days 1 to 42 postvaccination	Х	X	Х
	Injection-site reactions (redness, swelling, and pain/tenderness) Days 1 to 5 postvaccination	Х	X	Х
	Any AE Days 1 to 42 postvaccination		Х	Х
	Any serious AE Days 1 to 42 postvaccination		X	Х
	Any vaccine-related [§] AE Days 1 to 42 postvaccination		X	Х
	Any serious and vaccine-related [§] AE Days 1 to 42 postvaccination		X	Х
Tier 2	Discontinuation due to AE Days 1 to 42 postvaccination		Х	Х
	Specific systemic AEs [¶] and SOCs (incidence \geq 4 subjects in one of the vaccination groups) during Days 1 to 42 postvaccination and injection-site reactions [¶] (incidence \geq 4 subjects in one of the vaccination groups) Days 1 to 5 postvaccination and Days 1 to 42 postvaccination		x	Х

Table 4	Analysis	Strategy	for Safety	Parameters
Table 4	Analysis	Shalegy	for Safety	Farameters

Safety Tier	Safety Endpoint [†]	p Value	95% CI for Treatment Comparison	Descriptive Statistics
	Specific systemic AEs [¶] and SOCs (incidence <4 subjects in all of the vaccination groups) during Days 1 to 42 postvaccination and injection-site reactions [¶] (incidence <4 subjects in all of the vaccination groups) Days 1 to 5 and Days 1 to 42 postvaccination			Х
Tier 3	Maximum temperature summary (Brighton Collaboration Cutpoints) by day range: Days 1 to 42, Days 1 to 5, Days 6 to 13, Days 14 to 28, and Days 29 to 42 postvaccination			Х
	Distribution of maximum size (for injection-site redness and swelling Days 1 to 5 postvaccination) and distribution of maximum intensity (for all other injection-site reactions Days 1 to 5 postvaccination and all systemic AEs Days 1 to 42 postvaccination)			Х
	ience references refer to Clinical AEs.	. 1 . 1 .	1 / 1 11	
[‡] For reporting purposes, temperatures will be converted to oral equivalent by adding 1.0°F to axillary temperatures and subtracting 1.0°F from rectal temperatures.				
[§] Determined by the investigator to be related to the vaccine.				
[¶] Includes only those endpoints not pre-specified as Tier 1 or not already pre-specified as Tier-2 endpoints.				
\mathbf{V} = regults will be provided				

X = results will be provided.

The between-group comparisons described above will be made between Group 1 and Group 2 for each postvaccination follow-up period. This will be done by performing separate comparisons between VARIVAXTM PE34 process and VARIVAXTM (2016 commercial product) vaccination groups for the 42 days after receipt of the first vaccination and for the 42 days after receipt of the second vaccination. For serious adverse experiences, a summary along with a between-group comparison will also be provided for the entire primary trial phase (i.e., the combined 42-day periods after both vaccinations).

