4.2.3.2 Safety Endpoints

Throughout the clinical development program VARIVAX[™] has demonstrated an acceptable safety profile in children. Moreover, across dose ranges and manufacturing processes, aggregate safety data from the varicella clinical development program demonstrate the consistency of the safety profile of VARIVAXTM, with similar rates of local and systemic adverse experiences and temperature data. Additionally, in clinical studies that have evaluated the concomitant administration of VARIVAXTM with M-M-RTM II, concomitant use did not adversely affect the safety profile of either vaccine.

In clinical studies using a 2-dose regimen of VZV-containing vaccine in children, the incidence of injection-site reactions after vaccination was generally higher Postvaccination 2 than Postvaccination 1, although the injection-site reactions were short in duration and mild in intensity and size; whereas, significantly lower incidences of elevated temperatures and noninjection-site varicella-like rashes were observed Postvaccination 2 compared with Postvaccination 1.

As with previous VARIVAX[™] studies, the postvaccination safety follow-up period will be 42 days after each vaccination. The safety parameters for this trial will include the proportion of subjects with the following:

- 1) elevated temperatures $\geq 102.2^{\circ}$ F [$\geq 39.0^{\circ}$ C] oral equivalent) up to 42 days after each trial vaccination;
- 2) varicella-like, zoster-like, measles-like, or rubella-like rashes or mumps-like symptoms occurring up to 42 days after each trial vaccination;
- 3) solicited injection-site reactions (using the electronic vaccination report card [eVRC]), such as redness, swelling, and pain/tenderness/soreness, occurring within 5 days after each trial vaccination;

- 4) all unsolicited injection-site reactions occurring on Days 1 through 42 after each trial vaccination;
- 5) systemic adverse experiences up to 42 days after each trial vaccination;
- 6) serious adverse experiences throughout the trial duration; and
- 7) medically attended adverse events from Day 133 through Day 271.

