These subject exclusion criteria must be reviewed for each subject before Vaccination 2 to ensure that none of the criteria apply to the subject.

The subject must be excluded from receiving Vaccination 2 if the subject:

- 27. Has had any immunoglobulin, nonautologous blood, or blood products administered Postvaccination 1.
- 28. Has had any nontrial measles-, mumps-, rubella-, or VZV-containing vaccine administered Postvaccination 1.
- 29. Has received systemic immunomodulatory steroids (no more than the equivalent of >2 mg/kg total daily dose of prednisone or equivalent or >20 mg/day of prednisone or equivalent for subjects weighing >10 kg) for more than 7 consecutive days Postvaccination 1.
- 30. Has any blood dyscrasias, leukemia, lymphomas of any type, or other malignant neoplasms affecting the bone marrow or lymphatic systems diagnosed Postvaccination 1.
- 31. Has had any acquired or congenital immunodeficiency or active tuberculosis diagnosed Postvaccination 1.
- 32. Has had the occurrence of varicella infection Postvaccination 1.
- 33. Has had a vaccine-related allergic or anaphylactoid reaction reported Postvaccination 1.

- 34. Has enrolled in any other clinical trial other than a surveillance trial Postvaccination 1.
- 35. Has had a seizure, including a febrile seizure, Postvaccination 1.
- 36. Has had thrombocytopenia Postvaccination 1.

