7.1.2.1.5 Clinical Follow-up

Subjects will be followed for adverse events through 42 days after each vaccination. Specific injection-site reactions will be solicited from Day 1 through Day 5 after vaccination with the trial vaccine (VARIVAXTM PE34 or VARIVAXTM 2016 commercial product) and M-M-RTM II. Daily temperatures will be recorded on an eVRC from Day 1 through Day 42 after vaccination. Regardless of severity or causality, all unsolicited injection-site reactions; and all systemic adverse events, including varicella-, zoster-, measles-, rubella-like rashes and mumps-like symptoms, will be recorded on an eVRC for Day 1 through Day 42 after vaccination. Serious adverse events, including death, will be reported from Day 1 after the first dose of trial vaccine through Day 180 after the second dose of trial vaccine. Medically attended adverse events will be reported from Day 133 through Day 271. During the phone call at Day 271 (Day 180 Postvaccination 2), a scripted questionnaire will be used to determine if any serious adverse events or medically attended adverse events have occurred for each subject since completing the 42-day safety follow-up period Postvaccination 2.

The parent/legally acceptable representative of each subject will record the safety data on the eVRC and return the eVRC to the trial site at Visit 4. Trial personnel will review the eVRC for completeness, accuracy, and clarity. All information will be accurately recorded on the appropriate eCRFs.

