All adverse events that occur after the consent form is signed but before allocation/randomization must be reported by the investigator if they cause the subject to be excluded from the trial, or are the result of a protocol-specified intervention, including but not limited to washout or discontinuation of usual therapy, diet, placebo treatment or a procedure. From the time of allocation/randomization through 14 days (42 days for live attenuated vaccines) following the first vaccination(s) and from the time of any subsequent vaccination(s) through 14 days (42 days for live attenuated vaccines) thereafter, all adverse events must be reported by the investigator. Such events will be recorded at each examination on the Adverse Event case report forms/worksheets. The reporting timeframe for adverse events meeting any serious criteria is described in Section 7.2.2.1. The investigator will make every attempt to follow all subjects with non-serious adverse events for outcome.

Electronic reporting procedures can be found in the Electronic Data Capture (EDC) data entry guidelines. Paper reporting procedures can be found in the Investigator Trial File Binder (or equivalent).

7.2.1 Definition of an Overdose for This Protocol and Reporting of Overdose to the Sponsor

In this trial, an overdose is any dose higher than 1 dose of trial vaccine administered within 24 hours.

If an adverse event(s) is associated with ("results from") the overdose of Sponsor's product or vaccine, the adverse event(s) is reported as a non-serious adverse event, unless other serious criteria are met.

If a dose of Sponsor's product or vaccine meeting the protocol definition of overdose is taken without any associated clinical symptoms or abnormal laboratory results, the overdose is reported as a non-serious adverse event using the terminology "accidental or intentional overdose without adverse effect."

All reports of overdose with and without an adverse event must be reported by the investigator within 24 hours to the Sponsor either by electronic media or paper. Electronic reporting procedures can be found in the EDC data entry guidelines. Paper reporting procedures can be found in the Investigator Trial File Binder (or equivalent).

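### Table 4 counts discontinuation due to AE only for Days 1 to 42, so a later non-serious AE that stops dose 2 need not be reported and is not counted

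*Combined protocol and SAP*

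**What the plan says.** - **Endpoint.** Table 4 lists "Discontinuation due to AE Days 1 to 42 postvaccination" as a Tier 2 row. The text of Section 8.6.2 names the same endpoint without a day limit: subjects "and who discontinued due to an adverse experience will be considered Tier 2 endpoints". The end of that section confines the between-group comparisons to separate periods, "for the 42 days after receipt of the first vaccination and for the 42 days after receipt of the second vaccination".
- **Reporting.** Section 7.1.2.1.5 states: "Subjects will be followed for adverse events through 42 days after each vaccination". Section 7.2 makes all AEs reportable from randomization through 42 days after the first dose of a live vaccine, and again only from a subsequent vaccination. Section 4.2.3.2 adds "medically attended adverse events from Day 133 through Day 271". Only serious AEs are reportable continuously, to about 180 days after dose 2 (Section 7.2.2.1).
- **Stopping.** Section 5.1.3.2 lists events that bar dose 2, among them "Has had the occurrence of varicella infection Postvaccination 1" and "Has had a seizure, including a febrile seizure, Postvaccination 1". Neither has a day limit. The flow chart (Section 6.0) places the review of these criteria at Visit 3, and Section 5.8.1 requires vaccination to be discontinued when a Section 5.1.3 criterion is met.
- **Accounting.** Section 8.6.3 tabulates numbers vaccinated at each visit, and discontinuations and withdrawals per safety follow-up period. It does not ask for the AE behind a missed dose.

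**The concern.** With two doses, discontinuing vaccination because of an AE means not receiving dose 2. The plan looks for barring events over the whole interval after dose 1, but the endpoint meant to count the consequence closes on Day 42, and so does the duty to report a non-serious AE. A site following the text exactly could find at Visit 3 a non-serious varicella case that began on Day 60 and withhold dose 2. It would have no obligation to file an AE form, and the case would not enter the discontinuation row.

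At stake is the completeness of one between-group safety summary. For a varicella vaccine, non-serious varicella between doses is also an awkward event to leave without a required record. Sites may handle it differently, because the flow chart marks an AE review at Visit 3 while the reporting rule ended on Day 42.

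**Working it through.** **The plan's own figure.** Section 8.9.2 expects about 5% not to return for the second vaccination phase: 300 × (1 − 0.05) = 285 per group. This reproduces. It implies 300 − 285 = 15 children per group without dose 2, for all reasons together.

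**Inputs for the day count.** Dose 1 is on Day 1 and dose 2 on Days 91 to 105 (Section 5.2.2). The AE and endpoint window is Days 1 to 42 (Table 4, Section 7.1.2.1.5). Medically attended AEs start on Day 133 (Section 4.2.3.2).

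**Uncovered days** = (dose 2 day − 1) − 42, over an interval of (dose 2 day − 1):
- Dose 2 on Day 91: 90 − 42 = 48; 48/90 = 53.3%.
- Dose 2 on Day 105: 104 − 42 = 62; 62/104 = 59.6%.
- Dose 2 never given: reporting does not reopen, so Days 43 to 132 are uncovered, 132 − 43 + 1 = 90 days.

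Reading the limit as 42 days after Day 1 moves each count by one day and changes nothing of substance.

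**A non-serious AE that stops vaccination, by timing:**
- Onset by Day 42, stop decided by Day 42: must be reported and is counted.
- Onset by Day 42, stop decided at Visit 3: must be reported. It is counted if the Table 4 window dates AE onset, and missed if it dates the stop. The table does not say which.
- Onset from Day 43 to the dose 2 decision: not required to be reported and not counted, on either reading.

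The last case is the gap. It does not depend on how the row is read.

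**The case against.** The 42-day period is a deliberate choice, carried over from earlier studies of the product (Section 4.2.3.2) and used across the AE rows. Tier 2 intervals are descriptive by the plan's own statement. Both points stand. They limit the weight of this finding, but they do not explain why an endpoint about stopping a two-dose regimen should close well before the scheduled review of whether to stop.

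Several stronger readings are tempting, and the documents do not support them:

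- *Visit 3 is the only point at which vaccination can be stopped.* Section 5.8.1 allows discontinuation at any time. Visit 3 is only the scheduled review of the criteria.
- *Such events are never reported.* The flow chart marks an AE review at Visit 3, and a child who misses dose 2 still has the Visit 4 review. Section 7.1.4.1 asks that AEs present at discontinuation be followed, though under Section 7.2, which carries the 42-day limit. The accurate statement is that reporting is not required.
- *Seizures, thrombocytopenia and similar events disappear.* Some will be judged serious, including as other important medical events. They are then reported and compared over the whole trial.
- *Every stop decided at Visit 3 is missed.* This is true only if the row dates the stop. The neighbouring AE rows suggest that it dates the AE.
- *The row after dose 2 must be empty.* No vaccination remains to be stopped, but the text does not limit the endpoint to vaccination, so it may include discontinuation from the trial.
- *The 15 expected losses per group measure the under-count.* That figure concerns children who fail to return, for any reason. The share due to AEs is not given.
- *The between-group conclusion would change.* With 300 per group, the Miettinen-Nurminen statistic at zero difference is z = (x/300) / √[p(1 − p)(2/300)(600/599)], with p = x/600 for x versus 0 events. It gives 2.24 for 5 versus 0 and 1.73 for 3 versus 0, so losing two of five events would move the interval across zero. The counts are invented, and no trial decision rests on that interval.

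**Conclusion.** The concern holds in limited form. A non-serious AE with onset from Day 43 to the dose 2 decision that stops vaccination lies outside both required reporting and the Tier 2 row. The gap covers 53% to 60% of the inter-dose interval, assuming dose 2 in its Day 91 to 105 window. The missed dose would still show in the number vaccinated, but without its AE cause.

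The number of events lost cannot be derived from the documents. If every AE-driven stop had onset by Day 42 and the window dates onset, none would be lost. If onsets were spread evenly over the interval, which is an assumption without support in the plan, somewhat more than half would be. The primary hypotheses, sample size, power and alpha are unaffected. This is an inexpensive improvement to a named safety endpoint, together with a reconciliation of the Visit 3 AE review with the 42-day reporting rule.

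**What to change.** - **Sections 7.1.2.1.5 and 7.2:** require reporting of any AE that leads to discontinuation of vaccination, whatever its onset day, up to the dose 2 decision. State how this fits with the AE review that the flow chart places at Visit 3.
- **Section 8.6.2 and Table 4:** define the Tier 2 endpoint as discontinuation of vaccination due to an AE with onset from dose 1 through the dose 2 decision at Visit 3. State that the window refers to AE onset.
- **Leave unchanged:** the clinical criteria in Section 5.1.3 and its subsections.

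The cost is two protocol sentences, one table row and an eCRF instruction. Visit 3 already includes both reviews, and the AE evaluation in Table 2 already asks whether the event caused the vaccine to be discontinued, so families are asked for nothing new. The downsides are a few more AE forms and a window for this row that differs from the other 42-day rows, which a table footnote can explain.
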